4.5 Total Number of Subjects and Sites

The target number of completers will be N=56. We anticipate that about 20% of subjects (N=11) will terminate the study during the task because of discomfort and another 10% (N = 5) to withdraw due to scheduling issues. An additional 3 subjects per experiment (n=3) will be included for piloting.

4.6 Vulnerable Populations:

All subjects must be able to provide their own consent. This study is above minimal risk and we do not want to enroll participants who do not understand the risk/benefit ratio of the study, particularly when there is no benefit to the participants. For this reason we exclude people with IQ lower than 80. We exclude and rule out pregnant women because of the unknown effects of the shocks and of the fMRI on the developing fetus. We exclude non-English speakers since not all the instruments and test we use are translated and validated in Spanish or other languages. Based on our experience, we made the decision that 50 would be the upper age limit to prevent age-related changes in brain structure and function from confounding our analyses. Patients will not be taken off medications for the purpose of the study.

CONFIDENTIAL

5 Study Procedures

Does your study use MRI? (CAMRIS is the appropriate contact for all studies involving MRIs)

Yes No

Check of all that apply:

1.5T MRI
 3T MRI
 7TMRI

Does the MRI use investigational sequences and/or coils?
(See Experimental Device Clause)

Yes No Unsure (if unsure you need to contact CAMRIS)

Experimental Device Clause -- Some of the pulse sequences and/or RF coils are not FDA approved but are considered to pose no more than minimal risk.

Does your study include pregnant women?
(See Pregnancy Clause and Justification)

Yes No

Pregnancy Clause -- Although there are no known risks related to MRI on pregnant women or a fetus, there is a possibility of yet undiscovered pregnancy related risks. Since there is no possible benefit from participating in this protocol for a pregnant woman, we will exclude pregnant women.

Does the MRI require the use of Contrast Agents?
(See Contrast Risks)

Yes No

Does your study involve the exposure to radiation, radiotracers and/or radiological imaging modalities?

Yes No (If No, no RRSC review is needed)

Will any of the radiation exposure result from procedures that are or could be performed solely as a result of a subject's participation in the research protocol?

Yes No

CONFIDENTIAL

Ultrasound

Yes

No

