6.1 Primary Endpoints

Aim 1: Determine the effect of a 1-week course of TBS treatment (Continuous vs. Intermittent; right dlPFC target) on anxiety using the Neutral, Predictable, and Unpredictable (NPU) shock-threat paradigm.

Outcome measures. Fear potentiated startle (FPS) will be calculated by subtracting the blink magnitude during the predictable inter-trial interval (ITI) from the predictable cue. Anxiety potentiated startle (APS) will be calculated by subtracting the blink magnitude during the neutral ITI from the unpredictable ITI. Online anxiety ratings will be processed similarly.

Statistical Analysis. The main analysis will be a 3 [stimulation: pre-stimulation vs. post-active vs. post-sham] by 2 [protocol: cTBS vs. iTBS] repeated-measures ANOVA. In addition to the main factors considered, we may also co-vary out several individual difference measures (e.g. baseline anxiety via self-report questionnaires, counterbalance order, overall stimulation accuracy, and Sternberg working memory (WM) performance to assess target engagement).

Aim 2: Determine the effect of a 1-week course of TBS treatment (Continuous vs. Intermittent; right dlPFC target) on anxiety-related WM-deficits using the Sternberg WM paradigm during threat of shock.

Outcome measures. During each Sternberg trial, subjects will see a series of 5 or 8 letters presented singularly (encoding period) that will be followed by a brief interval where subjects are required to maintain these letters (maintenance period). At the end of the maintenance period, subjects will indicate whether the position of the letter in the series matches the number. Accuracy will be scored as the percent correct for each trial type.

Statistical Analysis. The main analysis will be a 3 [stimulation: pre-stimulation vs. post-active vs. post-sham] by 2 [protocol: cTBS vs. iTBS] repeated-measures ANOVA. As with Aim 1, we may also include several other individual difference measures as covariates in this analysis.

Aim 3: Demonstrate target engagement by measuring BOLD responses evoked by TMS pulses to the right dlPFC during threat of shock.

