6.2 Sample Size and Power Determination

Because we have several outcome measures, and because there is little known about how TMS will affect these outcome measures, we are conducting a single power analysis to determine sample size, based on a moderate effect size of ($f=0.5$). If we set power at 0.8 and use a corrected two-tailed alpha of 0.025 we would need 26 subjects per group to detect a main effect. Assuming a 15% unusable data rate and 3 pilot subjects, we will need 63 total subjects. However, this will be updated prior to enrollment based on the best available information at the time. To ensure that we are adequately powered across the study arms, and to account for additional dropout due to scheduling issues, we plan to recruit up to 75 participants.

7 Safety and Adverse Events

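### The repeated-measures ANOVA for Aims 1 and 2 has no rule for an unusable visit or for sphericity; a mixed model would handle both, with a modest gain in precision

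*Combined protocol and SAP*

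**What the plan says.** Section 6.1 gives the same main analysis for Aim 1 (startle) and Aim 2 (Sternberg performance): "The main analysis will be a 3 [stimulation: pre-stimulation vs. post-active vs. post-sham] by 2 [protocol: cTBS vs. iTBS] repeated-measures ANOVA". The synopsis repeats it. Both are silent on a missing or unusable visit, on sphericity, and on the covariance between visits. The optional covariates in 6.1 address none of these. Counterbalance order appears only as one of those optional covariates.

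Section 6.2 expects some data to be unusable: "Assuming a 15% unusable data rate and 3 pilot subjects, we will need 63 total subjects". The base is 26 per group ("we would need 26 subjects per group to detect a main effect"), at a two-sided level of 0.025. It then raises recruitment further ("to account for additional dropout due to scheduling issues, we plan to recruit up to 75 participants"). Section 4.5 gives a separate account of losses: "The target number of completers will be N=56", plus 11 stopping for discomfort, 5 lost to scheduling and 3 pilots.

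Section 7.5.1 separately removes pilots, withdrawals and subjects with an adverse event from the final analysis.

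**The concern.** Each subject is tested three times: in Week 1 and at the end of Weeks 2 and 4. A classical repeated-measures ANOVA uses only subjects with all three results. A subject who finishes the trial but has one bad EMG or Sternberg session therefore drops out entirely. That includes a subject whose only bad session is Week 1, although both visits needed for the sham-controlled comparison are in hand.

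The three-level F test also assumes sphericity (equal variances of the pairwise differences between visits). If this fails and no correction is made, the test rejects too often. With both matters unstated, the handling would be chosen after the data are seen, on the comparisons that answer Aims 1 and 2.

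The omnibus F is also not the question asked. Section 2 predicts a benefit over sham for excitatory but not inhibitory stimulation. That is a pair of active-minus-sham contrasts and their difference between protocols.

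**Working it through.** **1. What the 15% applies to.** Section 6.2 starts from 2 x 26 = 52 subjects. Then 52 x 1.15 = 59.8, and 59.8 + 3 = 62.8, which rounds to the stated 63. (Dividing instead, 52/0.85 = 61.2, rounded up to 62, plus 3 gives 65.) Going back, 63 - 3 = 60 and 60 x 0.85 = 51, about the planned 52. So the rate is used as a share of subjects. Whether 26 per group follows from the stated effect size is a separate question and is not needed here.

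**2. Subjects lost on that reading.** Assume unusable visits occur independently and 15% of subjects have at least one. The loss per visit is q = 1 - 0.85^(1/3) = 0.053.
- Complete on all three visits: 0.85. Of 56 completers, 56 x 0.85 = 47.6 enter the ANOVA.
- Both post-stimulation visits usable: (1 - q)^2 = 0.897.
- Dropped only because of Week 1: 0.897 - 0.85 = 0.047, or 56 x 0.047 = 2.6 subjects.

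**3. Gain in precision.** The complete-case variance of active minus sham is 2σ²(1 - ρ)/(0.85N). For the mixed model, the information is summed over missing-visit patterns: I = Σ p Z'(ZΣZ')⁻¹Z. The variance is c'I⁻¹c/N with c = (0, 1, -1). The correlation ρ is not in the documents; 0.3 to 0.7 is assumed, equal for all pairs.

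| Loss | SE ratio, mixed / complete-case | Equivalent extra subjects |
|---|---|---|
| 15% of subjects (5.3% per visit) | 0.953-0.958 | 9-10% |
| 15% of visits | 0.866-0.881 | 29-33% |

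The last column is 1/ratio² - 1; for example 1/0.958² = 1.09. In the first row, just over half the gain comes from subjects missing only Week 1: √(0.85/0.897) = 0.973. The rest comes from subjects with one post-stimulation visit. With balanced orders, active minus sham is orthogonal to Week 2 versus Week 4, so a period term leaves the expected ratios unchanged.

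The second row needs 15% per visit. Then 0.85³ = 0.614, and only 34.4 of 56 would be complete. Step 1 does not support that reading.

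**4. Power.** These are simulations of the stimulation-by-protocol interaction at level 0.025, with 60 subjects and 1,500 runs per cell. They assume a group difference in active minus sham of 0.9 SD of that difference, equal correlations of 0.5, and losses completely at random.

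| Loss | ANOVA | Mixed model, Kenward-Roger |
|---|---|---|
| None | 0.92 | 0.92 |
| 15% of subjects wholly unusable | 0.85 | 0.84 |
| 15% of subjects miss one visit | 0.86 | 0.87 |
| 15% of visits | 0.70 | 0.82 |

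The second and third rows differ only by simulation error.

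**5. Sphericity.** Let the pre-stimulation visit correlate a with each post-stimulation visit, and the two post-stimulation visits b with each other. The orthonormal contrasts have variances v1 = 1 - b and v2 = 1 - (4a - b)/3, and ε = (v1 + v2)²/[2(v1² + v2²)]. The error rates are for the uncorrected interaction F, 26 per group, 20,000 null trials, nominal 0.025.

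| a / a / b | v1, v2 | ε | Error rate |
|---|---|---|---|
| 0.5 / 0.5 / 0.5 | 0.5, 0.5 | 1 | 0.025 |
| 0.5 / 0.5 / 0.7 | 0.3, 0.567 | 0.91 | 0.029 |
| 0.4 / 0.4 / 0.8 | 0.2, 0.733 | 0.75 | 0.038 |
| 0.3 / 0.3 / 0.9 | 0.1, 0.9 | 0.61 | 0.047 |

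With Greenhouse-Geisser the rate was 0.023-0.027 throughout. With 60 subjects, the mixed model with Kenward-Roger gave 0.019-0.032 (simulation SE 0.004). A Wald chi-square in the same model gave 0.028-0.041, so the degrees-of-freedom method matters.

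**The case against.** The strongest reply is that the plan is silent rather than wrong, and that one sentence each on missing visits and sphericity would be enough. Several parts of it stand.

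- **Silence.** A reader might infer that the plan commits to an uncorrected F. It does not: section 6.1 neither applies nor rules out a correction. Dropping subjects with one bad visit is likewise how the named method usually works, not a written rule.
- **The loss is budgeted.** A reader might infer that nearly 40% of subjects would be lost. That needs 15% per visit, and the arithmetic in 6.2 enlarges the sample for a loss of subjects.
- **Strong non-sphericity is assumed.** No correlations are given. The first gap between tests is about 1-2 weeks and the second is 2 weeks, and order is counterbalanced. With correlation decaying over time (assumed 0.7-0.9 per week), ε was 0.957 or higher and the uncorrected F rejected 2.2-2.7% at nominal 2.5%. Large inflation needs an extra break between pre- and post-stimulation visits.
- **A mixed model is not the only way to hold the error rate.** Greenhouse-Geisser does so, and a one-degree-of-freedom active-minus-sham contrast with its own error term needs no sphericity.
- **Missing at random is open to doubt** in an anxiety task where about 20% are expected to stop for discomfort.

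These points limit the size of the concern but do not remove it. Greenhouse-Geisser retains no subjects and can cost power. In the simulation with correlations 0.4/0.4/0.8 and no missing data, power was 0.54 uncorrected, 0.45 with Greenhouse-Geisser and 0.85 with the mixed model. That contrast depends on the assumed correlations. The complete-case ANOVA generally needs a stronger missing-data assumption than the mixed model does.

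**Conclusion.** The point holds as a worthwhile, inexpensive improvement. The named ANOVA, in its usual form, discards usable active and sham results from completers and leaves sphericity open.

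On the reading that 6.2 supports, a mixed model gains at most a 4-5% smaller standard error for active minus sham. That assumes scattered, independent single-visit losses and correlations of 0.3-0.7. The gain is nil if bad data fall in whole subjects. A 12-13% gain would require 15% per visit.

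If no correction were applied, the error rate at nominal 0.025 would be about 0.029 under mild departures and 0.038-0.047 under the strong ones assumed above.

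A reader might also infer that the mixed model rescues the subjects expected to withdraw. It does not: section 7.5.1 excludes them, and subjects with an adverse event, whatever the model. That rule must be addressed separately.

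**What to change.** In 6.1 and the synopsis, replace the ANOVA with a linear mixed model fitted by REML:

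- Fixed effects: stimulation, protocol, their interaction, and period (test-visit order). The pre-stimulation test is always in Week 1, so period can only contrast Week 2 with Week 4. The term is needed once subjects with one post-stimulation visit are kept, because period effects then no longer cancel within subject.
- Unstructured covariance over the three test visits, with Kenward-Roger degrees of freedom.
- Every subject with at least one usable post-stimulation visit is included.
- Tested contrasts, named in advance: active minus sham within each protocol, and the difference between protocols.
- Sensitivity analysis: the complete-case ANOVA with Greenhouse-Geisser correction.

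In 6.2, state whether the 15% counts subjects or visits. Reconcile the inclusion rule with 7.5.1.

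The cost is SAP wording and slightly more analysis work, with no extra visits or subjects. The downside is reliance on data being missing at random, which the SAP should state.

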10.4	INFORMED CONSENT PROCESS / HIPAA AUTHORIZATION	23
11	STUDY FINANCES	23
11.1	FUNDING SOURCE.....	23
11.2	CONFLICT OF INTEREST	23
11.3	SUBJECT STIPENDS OR PAYMENTS	23
12	REFERENCES	24
13	ATTACHMENTS	29

CONFIDENTIAL

This material is the property of the University of Pennsylvania.

List of Abbreviations

adverse event (AE)
analysis of functional neuroimages AFNI
anxiety potentiated startle (APS)
anxiety-potentiated-BOLD AP-BOLD
bed nucleus of the stria terminalis (BNST)
case report form (CRF)
central nervous system (CNS)
cognitive paired-associate stimulation (C-PAS)
continuous theta-burst stimulation (cTBS)
dorsolateral prefrontal cortex (dlPFC)
electromyographic (EMG)
echo planar imaging (EPI)
Ethics Committee (EC)
Food and Drug Administration (FDA)
Fear potentiated startle (FPS)
first dorsal interosseus (FDI)
fear-potentiated-BOLD (FP-BOLD)
Health Insurance Portability and Accountability Act of 1996 (HIPAA)
high-frequency rTMS (HF-rTMS)
independent components analysis (ICA)
intermittent theta-burst stimulation (iTBS)
intertrial interval (ITI)
low-frequency rTMS (LF-rTMS)
motor evoked potential (MEP)
motor threshold (MT)
magnetic resonance imaging (MRI)
National Institute for Neurological Disorders and Stroke (NINDS)
neutral (N)
neutral predictable unpredictable threat task (NPU)
principle investigator (PI)
predictable shock (P)
protected health information (PHI)
repetitive TMS (rTMS)
serious adverse event (SAE)
echo time (TE)
Beck Anxiety Inventory (BAI)
State Anxiety Scale (S-Anxiety)
transcranial magnetic stimulation (TMS)
TMS adult safety screen (TASS)
Theta-burst stimulation TBS
unanticipated problem (UP)
unpredictable shock (U)
working memory (WM)

CONFIDENTIAL

Study Summary

Title Examining the mechanisms of anxiety regulation using a novel, sham-controlled, fMRI-guided rTMS protocol and a translational laboratory model of anxiety.

Short Title Effect of rTMS on anxiety

IRB Number 833320

Phase Pilot Study

Methodology Randomized, double-blinded, sham-controlled, cross-over design

Study Duration 4 years

Study Center(s) Single-center

Objectives

Aim 1: Determine the effect of a 1-week course of TBS treatment (Continuous vs. Intermittent; right dIPFC target) on anxiety using the unpredictable shock-threat paradigm.

Aim 2: Determine the effect of a 1-week course of TBS treatment (Continuous vs. Intermittent; right dIPFC target) on anxiety-related WM-deficits using the Sternberg WM paradigm during threat of shock.

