This research is significant because upon completion, we expect to have direct evidence for a causal role of the right dIPFC in anxiety regulation, complete with evidence

CONFIDENTIAL

of target engagement through simultaneous TMS/fMRI, and a novel application to anxiety. This research will lay the groundwork for my long-term career objective, which is to develop an independent, NIH-funded research program employing psychophysiology, neuroimaging, and neuromodulation in healthy and anxious participants aimed at developing a circuit-level understanding of the neurobiological mechanisms underlying anxiety.

2 Study Objectives

Aim 1: Determine the effect of a 1-week course of TBS treatment (Continuous vs. Intermittent; right dlPFC target) on anxiety using the unpredictable shock-threat paradigm. Our hypothesis, consistent with our pilot data, is that strengthening circuits in the right dlPFC will facilitate anxiety regulation. Accordingly, we expect excitatory but not inhibitory TBS (compared to sham) to reduce induced anxiety.

Aim 2: Determine the effect of a 1-week course of TBS treatment (Continuous vs. Intermittent; right dlPFC target) on anxiety-related WM-deficits using the Sternberg WM paradigm during threat of shock. Our hypothesis is that the rTMS will strengthen right dlPFC circuits, which will rescue the anxiety-related WM deficits. Accordingly, we expect that 10 Hz rTMS (compared to sham) will improve accuracy on the Sternberg WM task during threat.

Aim 3: Demonstrate target engagement by measuring BOLD responses evoked by TMS pulses to the right dlPFC during threat of shock. Our hypothesis is that direct stimulation of the right dlPFC will reduce ongoing anxiety-related activity. Accordingly, we expect active but not sham TMS pulses to the right dlPFC to evoke BOLD deactivations in regions of the fear/anxiety network (i.e. amygdala, BNST, anterior insula).

3 Investigational Plan

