3.1 General Design

Aims 1 and 2 of this project will be tested using a between-subjects design where 1 group of healthy volunteers will receive 4-day courses of active and sham cTBS stimulation to the right dlPFC, while the other group will receive 4-day courses of active and sham iTBS stimulation to the right dlPFC. In Aim 1, we will test the effects of this stimulation on anxiety during the NPU threat task. In Aim 2, we will test the effects of this stimulation on anxiety-related WM deficits using the Sternberg WM paradigm. In addition, we will also administer several self-report questionnaires to assess their baseline (pre-stimulation) anxiety. Subjects will be randomly assigned to groups, and the order of stimulation (active vs. sham) will be counterbalanced across subjects. Aim 3 will be tested using a within-subjects design where this same group of subjects will receive single-pulse active and sham stimulation to the right dlPFC during the NPU threat task while in the MRI scanner. BOLD activity to the TMS pulses will be the primary outcome measure.

Subjects will undergo 12 study visits spaced over a 4-week period (Figure 3). Subjects may also be offered an optional 13th visit where TMS/fMRI is conducted. On Week 1,

CONFIDENTIAL

subjects will undergo a pre-stimulation behavioral visit where they complete the NPU threat task and the Sternberg WM paradigm, and a pre-stimulation MRI visit where they undergo all the structural and functional imaging needed to identify the optimal target of stimulation for the course of TMS used in Aims 1 and 2. This information will be used to perform neuronavigation during the study visits to ensure accurate target stimulation. Subjects will complete the TMS/fMRI scans needed for Aim 3 during the optional visit. On Weeks 2 and 4, subjects will undergo 5 visits. The first 4 visits will be stimulation visits where they receive either active or sham stimulation while doing the Sternberg WM task. On the 5th visit, they will return for the post-stimulation test visit, where they will complete the NPU threat task and the Sternberg WM paradigm.

[figure not shown]

Figure 3: Timeline showing subject visits in the proposed project.

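### The active-versus-sham crossover prespecifies no period or sequence term, leaves order as an optional covariate, and does not address carry-over

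*Combined protocol and SAP*

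**What the plan says.** The Study Summary calls the trial "Randomized, double-blinded, sham-controlled, cross-over design". Section 3.1 randomises subjects to cTBS or iTBS and adds that "the order of stimulation (active vs. sham) will be counterbalanced across subjects". On timing it says "On Weeks 2 and 4, subjects will undergo 5 visits": four stimulation visits followed by a test visit. The payment schedule in section 11.3 shows no visits in Week 3. One course is therefore tested at Lab Visit 2 and the other at Lab Visit 3, and section 5.1 lists no new baseline before the second course.

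For both Aim 1 and Aim 2, section 6.1 states: "The main analysis will be a 3 [stimulation: pre-stimulation vs. post-active vs. post-sham] by 2 [protocol: cTBS vs. iTBS] repeated-measures ANOVA". For Aim 1 it continues: "we may also co-vary out several individual difference measures (e.g. baseline anxiety via self-report questionnaires, counterbalance order", among other examples. For Aim 2 it says only: "As with Aim 1, we may also include several other individual difference measures as covariates in this analysis". Order is not named again there.

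Section 2 gives the Aim 1 hypothesis, which "is that strengthening circuits in the right dlPFC will facilitate anxiety regulation". Section 4.5 anticipates that "about 20% of subjects (N=11) will terminate the study during the task because of discomfort", plus a further 10% lost to scheduling. Section 7.5.1 excludes subjects who withdraw or have an adverse event from the final analysis. Carry-over is not mentioned, and the length of the gap is not justified.

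**The concern.** Aims 1 and 2 rest on the within-subject difference between the post-active and post-sham tests. Those tests fall on different occasions, and which comes first is an assigned design factor, not a characteristic of the subject. Repeated startle testing and repeated Sternberg practice, including practice during the stimulation visits, could move scores between Lab Visits 2 and 3. A model without period leaves that movement in the error of the key contrast. Because order adjustment is optional, the decision can also be taken after the results are known.

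Carry-over is a separate matter. The premise is that stimulation strengthens a circuit. In active-first subjects the sham test follows the active course, so any lasting effect would reduce the difference being estimated. The plan commits to no analysis that bears on this.

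**Working it through.** **The plan's own figure.** Section 6.2 gives 26 per group for f = 0.5, two-tailed alpha 0.025 and power 0.80. A fixed-effects 3 × 2 ANOVA with independent cells and 2 numerator df needs 51 in total, hence 26 per group. Then 52 × 1.15 = 59.8, rounded to 60, plus 3 pilots gives the stated 63. A paired t-test at a standardised difference of 0.5 would need 41. The stated size therefore reproduces, but not from the paired contrast studied here. Below I keep 26 per group and alpha 0.025, and set the effect at 0.638 SD of the difference, which 26 paired observations detect with 80% power.

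**Model.** Let D = active − sham, with SD 1, true effect tau, and pi the shift from Lab Visit 2 to Lab Visit 3 in those SD units.

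- Active first: mean of D = tau − pi.
- Sham first: mean of D = tau + pi.

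**Balanced orders (13/13).** The mean of D is tau, so there is no bias. The pooled variance is 1 + pi², so the SE ratio is sqrt(1 + pi²) and the equivalent sample is 26/(1 + pi²). Power and type I error are simulated.

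| pi (assumed) | SE ratio | Acts like | Power without term | Power with term | Type I error without term |
|---|---|---|---|---|---|
| 0.25 | 1.03 | 24 | 78% | 80% | 2.1% |
| 0.5 | 1.12 | 21 | 71% | 80% | 1.3% |
| 1.0 (unfavourable) | 1.41 | 13 | about 45% | 80% | 0.2% |

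With 28 per protocol (half of the 56 target completers in section 4.5), power is 84% with no shift. At pi = 0.5 it is 76% without the term and 83% with it.

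**Unbalanced orders.** Bias = pi × (n sham-first − n active-first)/n. In absolute size:

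- 15/11: 4/26 = 0.15 × pi. At pi = 0.5 this is 0.077, or 12% of 0.638.
- 16/10: 6/26 = 0.23 × pi. At pi = 0.5 this is 0.115, or 18% of 0.638.

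To see how likely such splits are, take 75 recruits less 3 pilots = 72, or 36 per protocol. Assume they start 18/18 by order and 10 are lost at random, leaving 26. The hypergeometric distribution gives a split of 15/11 or worse about 26% of the time and 16/10 or worse about 6%. The mean absolute bias is about 0.08 × pi. Averaging the two order-specific means of D with equal weight, as a sequence term does, removes this bias.

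**Carry-over.** If a fraction c of the active effect persists into the sham test, active-first subjects have mean D = tau(1 − c) − pi and sham-first subjects are unchanged. The average is tau(1 − c/2).

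- c = 0.1: 5% attenuation, power about 75%.
- c = 0.25: 12.5% attenuation, power about 67%.
- c = 0.5: 25% attenuation, power about 52–53%.

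These results are almost the same with or without the sequence term.

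**How the order covariate is entered.** An order main effect alone is constant within a subject and cancels in D. Only order with its interaction with stimulation absorbs the shift; that interaction is the period effect.

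**Precision of a Lab Visit 2-only comparison.** Assume equal variances and one correlation rho between visits. The variance of the baseline-adjusted comparison of 13 with 13 is (1 − rho²) × 2/13, and that of the crossover estimate is 2(1 − rho)/26. The SE ratio is sqrt(2(1 + rho)): 1.61 at rho = 0.3, 1.73 at 0.5 and 1.84 at 0.7.

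**The case against.** Several points on the other side are sound.

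- **Order is not ignored.** Section 6.1 names it, and the Aim 2 text refers back to Aim 1. A reader might infer that the plan has no means of handling order. The documents do not support that. The defect is that its use is optional and its form is unspecified.
- **The shift may be small.** FPS and APS are within-session differences, so a purely additive fall in startle cancels; a proportional fall would not. Each test visit repeats the noise habituation and shock workup. Before Lab Visit 2, subjects have already done the Sternberg task at Lab Visit 1, in the MRI localiser runs and at four stimulation visits. This argues against pi near 1 but does not make pi zero.
- **The error is conservative.** With balanced orders the cost is lost power, not false positives. This stands.
- **Imbalance may be mild.** Nothing says that withdrawal depends on order, and some discomfort exits may precede any stimulation. The 16/10 split is an unfavourable case.
- **Carry-over is hypothetical.** Strengthening a circuit is a mechanism, not a duration, and the documents give no duration of after-effect. If visits fall on consecutive weekdays (an assumption), about 15 days separate the last active pulse from the sham test in active-first subjects. A reader might infer that the sham results are contaminated, or that the crossover estimate is a lower bound. Neither is supported. With no carry-over at all, a Lab Visit 2-only estimate would exceed the crossover estimate about half the time by chance.

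None of this gives a reason to leave period and sequence out.

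**Conclusion.** The point holds as a gap in prespecification with a modest, assumption-dependent cost. As written, the main analysis lets any shift between Lab Visits 2 and 3 remain in the active-minus-sham error. For plausible shifts of 0.25 to 0.5 SD, power falls from 80% to about 78% and 71%; pi = 1 is only an outer case. A reader might infer that the contrast is biased by design. It is not biased by period while the orders are balanced. Bias enters only if exclusions unbalance the orders (0.15 × pi at 15/11, 0.23 × pi at 16/10) or if carry-over exists (attenuation by c/2). A period term removes the first source and not the second.

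The results rest on assumed values of pi and c, a 1:1 split of orders, 26 per group, and random loss of 10 from 36. The change should be made because it is nearly free and closes an analytic choice. It does not show that the trial's conclusions would be wrong.

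**What to change.** 1. Take counterbalance order out of the optional covariates. In the active-versus-sham analysis for Aims 1 and 2, make period (Lab Visit 2 versus Lab Visit 3) and sequence fixed terms. Entering order together with its interaction with stimulation is equivalent. The pre-stimulation visit always comes first, so these terms concern the two post-stimulation tests only.
2. Prespecify one descriptive sensitivity estimate with its confidence interval: Lab Visit 2 only, active-first versus sham-first within each protocol, adjusted for the Lab Visit 1 score. State that it is imprecise. Do not use it as a pretest for carry-over, to choose between analyses, or to reinterpret the crossover estimate as a lower bound. A formal carry-over test would be of little use: with 13 per order and c = 0.5, its power at alpha 0.05 is about 6–9% for correlations of 0.3 to 0.7.

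The cost is plan wording, one degree of freedom per group (power 80% either way when there is no shift), and one extra model on data already collected. No visits, subjects or procedures change.
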